#### 12.5.1.7 Non-Physical Risks of Genetic Research

##### 12.5.1.7.1 ***Risk of receiving unwanted information***

Anxiety and stress may arise as a result of the anticipation that unwanted information regarding disease related DNA sequencing or disease tendencies, or misattributed paternity. Patients will be clearly informed that the data related to DNA sequencing and genetic analysis is coded, investigational and will not be shared with patients, family members or health care providers.

##### 12.5.1.7.2 ***Risk related to possibility that information may be released***

This includes the risk that data related to genotype, DNA sequencing or risk for disease tendency or trait can be released to members of the public, insurers, employers, or law enforcement agencies. Although there are no plans to release results to the patients, family members or health care providers, this risk will be included in the informed consent document.

##### 12.5.1.7.3 ***Risk to family or relatives***

Family members or relatives may or may not want to be aware of familial tendencies or genetic risks of disease which may cause anxiety about possible future health problems. As previously noted, patients will be notified of any medically significant and actionable incidental findings. Study results will not be shared with patients.

### 12.5.2 Known Potential Benefits

Patients who previously received checkpoint therapy may benefit from receiving further checkpoint block with M7824 they would otherwise not obtain in a standard of care setting. Immediate potential benefits include potential response to tumor progression, palliation of symptoms, and improved outcomes. Long range potential benefits of this study will build on knowledge and the science used to develop therapies for future cancer patients

### 12.5.3 Assessment of Potential Risks and Benefits

A number of clinically appropriate strategies to minimize risk to patients have been built into the protocol through the means of inclusion/exclusion criteria, monitoring strategies, and management guidelines. Overall, the potential benefits of M7824 for patients retaining the ability to consent and those who lose capacity to consent during the course of the trial outweigh the risks associated with the proposed entry into this trial.

## 12.6 CONSENT PROCESS AND DOCUMENTATION

The informed consent document will be provided as a physical or electronic document to the participant or consent designee(s) as applicable for review prior to consenting. A designated study investigator will carefully explain the procedures and tests involved in this study, and the associated risks, discomforts and benefits. In order to minimize potential coercion, as much time as is needed to review the document will be given, including an opportunity to discuss it with friends, family members and/or other advisors, and to ask questions of any designated study investigator. A signed informed consent document will be obtained prior to entry onto the study.

The initial consent process as well as re-consent, when required, may take place in person or remotely (e.g., via telephone or other NIH approved remote platforms used in compliance with policy, including HRPP Policy 303) per discretion of the designated study investigator and with the agreement of the participant/consent designee(s). Whether in person or remote, the privacy of the subject will be maintained. Consenting investigators (and participant/consent designee, when in person) will be located in a private area (e.g., clinic consult room). When consent is conducted remotely, the participant/consent designee will be informed of the private nature of the discussion and will be encouraged to relocate to a more private setting if needed.

Note: When required, witness signature will be obtained similarly as described for the investigator and participant as described below.

Consent will be documented with required signatures on the physical document (which includes the printout of an electronic document sent to participant) or on the electronic document. Signatures on electronic documents are described below. Note: FDA only regulates electronic signatures (i.e., an electronic timestamp is generated at the time of signature) in FDA regulated research.

#### Manual (non-electronic) signature on electronic document:

When a manual signature on an electronic document is used for the documentation of consent at the NIH Clinical Center, this study will use the Adobe platform (which is not 21 CFR Part 11 compliant) to obtain the required signatures.

During the consent process, participants and investigators will view individual copies of the approved consent document on screens at their respective locations.

Both the investigator and the subject will sign the document with a hand signature using a finger, stylus or mouse.

#### *Electronic signature on electronic document*

When permitted by the NIH Clinical Center, electronic signatures may be obtained using the iMedConsent platform once it is designated as 21 CFR Part 11 compliant.

During the consent process, participants and investigators will view individual copies of the approved consent document on screens at their respective locations.

The identity of the participant will be determined by a prompt which will require the provision of information from a form of government issued identification prior to obtaining the signature. If participant does not have such identification available, security questions will be used to confirm identity.

Both the investigator and the subject will sign the document electronically per system prompts.

#### 12.6.1 Consent Process for Adults Who Lack Capacity to Consent to Research Participation

For participants addressed in Section 12.3, an LAR will be identified consistent with Policy 403 and informed consent obtained from the LAR, as described in Section 12.6.

## **13 REGULATORY AND OPERATIONAL CONSIDERATIONS**

### **13.1 STUDY DISCONTINUATION AND CLOSURE**

This study may be temporarily suspended or prematurely terminated if there is sufficient reasonable cause. Written notification, documenting the reason for study suspension or termination, will be provided by the suspending or terminating party to study participants, investigator, funding agency, the Investigational New Drug (IND) sponsor and regulatory authorities. If the study is prematurely terminated or suspended, the Principal Investigator (PI) will promptly inform study participants, the Institutional Review Board (IRB), and sponsor and will provide the reason(s) for the termination or suspension. Study participants will be contacted, as applicable, and be informed of changes to study visit schedule.

Circumstances that may warrant termination or suspension include, but are not limited to:

- Determination of unexpected, significant, or unacceptable risk to participants
- Demonstration of efficacy that would warrant stopping
- Insufficient compliance to protocol requirements
- Data that are not sufficiently complete and/or evaluable
- Determination that the primary endpoint has been met
- Determination of futility

Study may resume once concerns about safety, protocol compliance, and data quality are addressed, and satisfy the sponsor, IRB and, as applicable, Food and Drug Administration (FDA).

### **13.2 QUALITY ASSURANCE AND QUALITY CONTROL**

The clinical site will perform internal quality management of study conduct, data and biological specimen collection, documentation and completion. An individualized quality management plan will be developed to describe a site's quality management.

Quality control (QC) procedures will be implemented beginning with the data entry system and data QC checks that will be run on the database will be generated. Any missing data or data anomalies will be communicated to the site(s) for clarification/resolution.

Following written Standard Operating Procedures (SOPs), the monitors will verify that the clinical trial is conducted and data are generated and biological specimens are collected, documented (recorded), and reported in compliance with the protocol, International Conference on Harmonisation Good Clinical Practice (ICH GCP), and applicable regulatory requirements (e.g., Good Laboratory Practices (GLP), Good Manufacturing Practices (GMP)).

The investigational site will provide direct access to all trial related sites, source data/documents, and reports for the purpose of monitoring and auditing by the sponsor, and inspection by local and regulatory authorities.

### **13.3 CONFLICT OF INTEREST POLICY**

The independence of this study from any actual or perceived influence, such as by the pharmaceutical industry, is critical. Therefore, any actual conflict of interest of persons who have a role in the design, conduct, analysis, publication, or any aspect of this trial will be disclosed and managed. Furthermore, persons who have a perceived conflict of interest will be required to have such conflicts managed in a way that is appropriate to their participation in the design and conduct of this trial. The study leadership in conjunction with the NCI has established policies and procedures for all study group members to disclose all conflicts of interest and will establish a mechanism for the management of all reported dualities of interest.

### **13.4 CONFIDENTIALITY AND PRIVACY**

Participant confidentiality and privacy is strictly held in trust by the participating investigators, their staff, and the sponsor(s). This confidentiality is extended to cover testing of biological samples and genetic tests in addition to the clinical information relating to participants. Therefore, the study protocol, documentation, data, and all other information generated will be held in strict confidence. No information concerning the study or the data will be released to any unauthorized third party without prior written approval of the sponsor.

All research activities will be conducted in as private a setting as possible.

The study monitor, other authorized representatives of the sponsor, representatives of the Institutional Review Board (IRB), and/or regulatory agencies may inspect all documents and records required to be maintained by the investigator, including but not limited to, medical records (office, clinic, or hospital) and pharmacy records for the participants in this study. The clinical study site will permit access to such records.

The study participant's contact information will be securely stored at the/each clinical site for internal use during the study. At the end of the study, all records will continue to be kept in a secure

*Abbreviated Title: Phase II M7824 in UC*

*Version Date: 06/23/2021*

location for as long a period as dictated by the reviewing IRB, Institutional policies, or sponsor requirements.

Study participant research data, which is for purposes of statistical analysis and scientific reporting, will be stored at the NCI CCR. This will not include the participant's contact or identifying information. Rather, individual participants and their research data will be identified by a unique study identification number. The study data entry and study management systems used by the clinical site(s) and by NCI CCR research staff will be secured and password protected. At the end of the study, all study databases will be archived at the NIH.

To further protect the privacy of study participants, a Certificate of Confidentiality has been issued by the National Institutes of Health (NIH). This certificate protects identifiable research information from forced disclosure. It allows the investigator and others who have access to research records to refuse to disclose identifying information on research participation in any civil, criminal, administrative, legislative, or other proceeding, whether at the federal, state, or local level. By protecting researchers and institutions from being compelled to disclose information that would identify research participants, Certificates of Confidentiality help achieve the research objectives and promote participation in studies by helping assure confidentiality and privacy to participants.

## **14 PHARMACEUTICAL AND INVESTIGATIONAL DEVICE INFORMATION**

### **14.1 M7824 (BINTRAFUSP ALFA, MSB0011359C) (IND # 149968)**

#### 14.1.1 Source/Acquisition and Accountability

M7824 is manufactured and supplied for the trial by EMD Serono Research and Development Institute. The investigational product will be dispensed at the direction of an investigator for administration to a study participant enrolled on the clinical trial. Disposal of expired or unused product will be returned to the manufacturer or disposed of according to standard site procedures based on agreement between the manufacturer and the site.

#### 14.1.2 Toxicity

In a phase 1, open-label 3+3 dose-escalation study of M7824 in 16 patients, 3 patients experienced grade 3 drug-related adverse events including skin infection secondary to grade 2 cccc, lipase increased, and colitis with associated anemia. There were no grade 4 – 5 treatment related adverse events. Please see table below for details:

Abbreviated Title: Phase II M7824 in UC  
Version Date: 06/23/2021

**Treatment-related TEAE Leading to Permanent Treatment Discontinuation by System Organ Class and Preferred Term in  $\geq 2$  participants in the Pooled Analysis of Dose Expansion Cohorts (Source: Investigator Brochure v6)**

Primary System Organ Class Dictionary-Derived Term	EMR200647-001 (N = 539) N (%)	MS200647-0008 (N = 91) N (%)	Total (N = 630) N (%)
Participants with any SAE	321 (59.6)	50 (54.9)	371 (58.9)
Blood and lymphatic system disorders	27 (5.0)	0	27 (4.3)
Anaemia	19 (3.5)	0	19 (3.0)
Endocrine disorders	11 (2.0)	2 (2.2)	13 (2.1)
Adrenal insufficiency	5 (0.9)	2 (2.2)	7 (1.1)
Gastrointestinal disorders	64 (11.9)	13 (14.3)	77 (12.2)
Abdominal pain	5 (0.9)	1 (1.1)	6 (1.0)
Gastrointestinal haemorrhage	7 (1.3)	1 (1.1)	8 (1.3)
Upper gastrointestinal haemorrhage	2 (0.4)	4 (4.4)	6 (1.0)
Vomiting	6 (1.1)	0	6 (1.0)
General disorders and administration site conditions	70 (13.0)	10 (11.0)	80 (12.7)
Disease progression	43 (8.0)	6 (6.6)	49 (7.8)
General physical health deterioration	6 (1.1)	0	6 (1.0)
Pyrexia	8 (1.5)	1 (1.1)	9 (1.4)
Hepatobiliary disorders	10 (1.9)	8 (8.8)	18 (2.9)
Cholangitis	2 (0.4)	5 (5.5)	7 (1.1)
Infections and infestations	54 (10.0)	9 (9.9)	63 (10.0)
Pneumonia	14 (2.6)	3 (3.3)	17 (2.7)
Sepsis	8 (1.5)	0	8 (1.3)
Metabolism and nutrition disorders	25 (4.6)	3 (3.3)	28 (4.4)
Decreased appetite	5 (0.9)	3 (3.3)	8 (1.3)
Neoplasms benign, malignant and unspecified (incl cysts and polyps)	61 (11.3)	8 (8.8)	69 (11.0)
Keratoacanthoma	9 (1.7)	0	9 (1.4)
Squamous cell carcinoma of skin	22 (4.1)	1 (1.1)	23 (3.7)
Tumour haemorrhage	8 (1.5)	2 (2.2)	10 (1.6)
Renal and urinary disorders	14 (2.6)	0	14 (2.2)
Acute kidney injury	10 (1.9)	0	10 (1.6)
Respiratory, thoracic and mediastinal disorders	68 (12.6)	6 (6.6)	74 (11.7)
Dyspnoea	26 (4.8)	0	26 (4.1)
Pneumothorax	6 (1.1)	1 (1.1)	7 (1.1)
Pulmonary embolism	9 (1.7)	0	9 (1.4)

IRR is a composite term which includes Reactions: Anaphylactic reaction, Drug hypersensitivity, Hypersensitivity, Infusion related reaction, Type I hypersensitivity and Signs and Symptoms: Abdominal pain, Back pain, Chills, Dyspnoea, Flushing, Hypotension, Pyrexia, Urticaria, Wheezing.

irAEs identified risk for M7824 (based on PDL-1blockade) are Thyroiditis, autoimmune thyroiditis, hypothyroidism, hyperthyroidism, Diabetes mellitus, Type I diabetes, type I diabetes mellitus, adrenal insufficiency, adrenalitis, Colitis Enteritis, enterocolitis, Nephritis, acute kidney injury, Myositis, Retinal microvasculitis, retinal vasculitis, rash, rash generalized, maculo-papular rash, erythematous, rash, pruritic rash, pemphigoid, Pneumonitis Interstitial pneumonitis, Interstitial lung disease.

irAEs potential risks for M7824 are Guillain-Barré syndrome, uveitis, pancreatitis, myasthenia gravis/myasthenic syndrome.

Skin AE ( TGF- $\beta$  blockade mediated) include rash with hyperkeratosis, cutaneous squamous cell carcinoma, keratoacanthoma.

*Abbreviated Title: Phase II M7824 in UC*

*Version Date: 06/23/2021*

Important potential risks includes treatment related anemia, delay in wound healing and embryofetal toxicity.

As of October 2018, more than 670 patients have been treated with M7824 1200mg flat dose q2w across multiple solid tumor expansion cohorts.

The safety profile is consistent with other monotherapy checkpoint inhibitors, with the exception of keratoacanthomas and cutaneous squamous cell carcinomas ( similar to anti-TGF- $\beta$  targeting therapy Fresolimumab and TGF- $\beta$  genetic mutation inheritance -Ferguson- Smith Syndrome) which have occurred in approximately 7% of M7824 treated patients, and are well managed with surgical excision. These lesions have not been a criterion for treatment discontinuation.

In addition, after discussion among NCI investigators on multiple protocols using M7824, multiple bleeding events ranging from low grade gingival bleeding and epistaxis to more serious hemoptysis, mild and moderate mucosal bleedings, GI bleeding and hematuria have been observed. Some of these events can be attributed to bleeding events related to cancer directly and others bleeding events can be attributed to colitis or cystitis which is a known toxicity of anti-PD-L1 agents including M7824. However, there remains the possibility that M7824 may increase the overall risk of bleeding in ways that may not be directly related to direct tumor bleeding or inflammatory bleeding events described with checkpoint inhibitors like M7824. It is hypothesized that this possible increased bleeding risk may be due to TGF beta inhibition which has an effect on angiogenesis; bleeding has also been observed in patients receiving M7824 and may be drug-related (e.g., gum bleeding, nose bleeds, coughing up blood, blood in their urine, or blood in the stool). Accordingly, patients will be notified of the same possible risk in the informed consent document for this study (e.g., gum bleeding, nose bleeds, coughing up blood, blood in their urine, or blood in the stool).

#### 14.1.3 Formulation and preparation

M7824 drug product is provided as a sterile liquid formulation.

The Concentrate for Solution for Infusion (liquid formulation) is packaged at a 10 mg/mL concentration in USP / Ph. Eur. type I 50R or 20R vials which are filled with drug product solution to allow an extractable volume of 60 mL (600 mg/60 mL). The vials are closed with rubber stoppers with the same composition as used for freeze-dried formulation, but in serum format complying with USP and Ph. Eur. with an aluminum crimp seal closure.

#### 14.1.4 Stability and Storage

M7824 drug product must be stored at 2°C to 8°C until use. The storage condition is based on data from ongoing long term stability studies with M7824.

M7824 drug product stored at room (23°C to 27°C) or higher temperatures for extended periods of time might be subject to degradation.

The liquid formulation is diluted directly with 0.9% saline solution. The chemical and physical in-use stability for the infusion solution of M7824 in 0.9% saline solution has been demonstrated for a total of 72 hours at 2°C to 8°C and 24 hours at room temperature. However, from a microbiological point of view, the diluted solution should be used immediately and is not intended to be stored unless dilution has taken place in controlled and validated aseptic conditions. If not

used immediately, in-use storage times and conditions prior to administration are the responsibility of the user. Do not freeze or shake the diluted solution.

No other drugs should be added to the infusion containers containing M7824.

#### 14.1.5 Administration procedures

M7824 will be administered as a 1-hour intravenous (IV) infusion once every two weeks of each cycle. M7824 is administered as IV infusion via a peripheral or central vascular access device (VAD). Confirm patient has a port with titanium as the main material before accessing the Central VAD. A 0.2 micron polyethersulfone (PES) in-line filter is mandatory for administration. Premedications may be administered per Section [3.3.1.1](#).

As with all monoclonal antibody therapies, there is a risk of allergic reaction including anaphylactic shock. M7824 should be administered in a setting that allows for immediate access to an intensive care unit or equivalent environment and administration of therapy for anaphylaxis, such as the ability to implement immediate resuscitation measures. Steroids (dexamethasone 10 mg), epinephrine (1:1,000 dilution), allergy medications (IV antihistamines), bronchodilators, or equivalents, and oxygen should be available for immediate access.

Patients must be observed for 2 hours after the first M7824 dose. If no reactions are observed, the patients need to be monitored for only 30 minutes after subsequent doses.

If an allergic reaction occurs, the subject must be treated according to the best available medical practice. Please see the guidelines for handling of infusion-related reaction in Section [3.3.1.4](#).

Investigators should also monitor subjects closely for potential irAEs, which may become manifest after several weeks of treatment. Such events may consist of persistent rash, diarrhea and colitis, autoimmune hepatitis, arthritis, glomerulonephritis, cardiomyopathy, or uveitis and other inflammatory eye conditions.

Vital signs must be measured within 30 minutes before and 30 minutes following M7824 infusions. In addition, at least one time during the infusion of M7824.

#### 14.1.6 Incompatibilities

None known

## 16 APPENDICES

### 16.1 APPENDIX A: STUDY CALENDAR

	Screening 	All Cycles (28 days each)												EOT visit	Follow up 	
		C1 D1	C1 D15	C2 D1	C2 D15	C3 D1	C3 D15	C4 D1	C4 D15	C5 D1	C5 D15	C6 D1	C6 D15 & Beyond			
History/PE incl weight and skin assessment 	X	X	X	X	X	X	X	X	X	X	X	X	X	X	X	
Confirmation of pathology/Biopsy 	X					X									X	
ECOG, Vital Signs	X	X	X	X	X	X	X	X	X	X	X	X	X	X	X	
Tumor evaluation/measurements	X					X				X			X 			
M7824 		X	X	X	X	X	X	X	X	X	X	X	X	X		
Lab assessments 	X	X	X	X	X	X	X	X	X	X	X	X	X	X	X	X
Pregnancy test 	X	X		X		X		X		X		X				
Lymphocyte phenotyping 	X															
ECG	X															
CT C/A/P or CT C+MRI A/P 	X					X				X			X 	X		
Follow-up Phone calls/emails																X 
Correlative Studies	Please refer to Section 5.2															

*Abbreviated Title: Phase II M7824 in UC*  
*Version Date: 06/23/2021*

1. Pre-treatment tissue biopsy and/or tissue availability is mandatory. On-treatment biopsy is required unless obtaining biopsy is not technically or clinically feasible. Post-treatment biopsy is optional.
2. Tests done at screening do not need to be repeated on baseline (C1D1) if performed within 21 days prior to initiation of study therapy.
3. M7824 will be delivered intravenously every 2 weeks (+/- 3 days).
4. Vital signs must be measured within 30 minutes before and 30 minutes following M7824 infusions. In addition, at least one time during the infusion of M7824.
5. Laboratory assessments: CBC with differential, acute care panel (sodium, potassium, chloride, total CO2 (Bicarbonate), creatinine, glucose, urea nitrogen), mineral panel (albumin, calcium total, magnesium total, phosphorus), hepatic panel (alkaline phosphatase, ALT/GPT, AST/GOT, total bilirubin, direct bilirubin), ionized calcium, amylase, lipase, TSH with reflex T3 and T4, LDH, total protein, GGT, PT/INR, PTT, and urine analysis. Hepatitis B and C will be done at screening only.
6. For females of childbearing-potential (within 3 days prior to initiation of study therapy).
7. Lymphocyte phenotyping tests will be done to check the eligibility of HIV positive patients. HIV-positive patients are eligible only if CD4 counts are greater than 350 cells/mm^3 and viral load is undetectable.
8. CT of chest, abdomen and pelvis with IV contrast (oral contrast as indicated) or CT of the chest without contrast and MRI abdomen/pelvis with tumor measurements. For this study patients should be re-evaluated for response every 8 weeks (+/- 10 days). If a scan identifies objective response or progressive disease, a confirmatory scan should be obtained 4-8 weeks following initial documentation of objective response or progression. In patients with clinical progression or unequivocal scan, confirmatory progression scan can be deferred. Scans will continue every 8 weeks until disease progression or start of a new anti-cancer treatment.
9. After disease progression or in those subjects who were removed from study therapy for reasons other than disease progression, subjects will be followed every 12 weeks in clinic or by telephone/email for assessment of survival status, related adverse events and documentation of initiation of new anti-cancer therapy.
10. If appropriate screening imaging is done within 21 days of C1D1 repeat screening imaging is not required.
11. All SAEs ongoing at the 30-day (+/- 10 days) safety follow-up visit must be monitored and followed up by the investigator until stabilization or until the outcome is known, unless the subject is documented as "lost to follow-up." In addition, all trial drug-related SAEs occurring after 30 day safety follow up visit and ongoing at the Safety Follow-up visit have to be followed up in the same manner.
12. Skin assessment must be performed at baseline and at least every 6 weeks during treatment and at the end of treatment or 28 (±5 days) days post-treatment safety follow-up (if not performed in the previous 6 weeks).

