- 2.1.4 Cohort 2A Checkpoint Inhibitor Previously Treated Patients that Previously Achieved a Complete Response (CR) or Partial Response (PR) Specific Inclusion Criteria
- Patients must have been treated with at least one treatment of a PD-1/PD-L1 checkpoint inhibitor for advance or metastatic UC and achieved a complete response or partial response by RECIST 1.1 criteria.
- 2.1.5 Cohort 2B Checkpoint inhibitor previously treated patients that previously had stable disease (SD) or progressive disease (PD)
- 2.1.6 Specific Inclusion Criteria
- Patients must have been treated with at least one treatment of a PD-1/PD-L1 checkpoint inhibitor for advance or metastatic UC and had stable disease or a progressive disease by RECIST 1.1 criteria.
- 2.1.7 Exclusion Criteria
- 2.1.7.1 History of allergic reactions attributed to compounds of similar chemical or biologic composition to M7824 investigational agents used in the study.
- 2.1.7.2 Uncontrolled intercurrent illness including, but not limited to, symptomatic congestive heart failure, unstable angina pectoris, cardiac arrhythmia, or psychiatric illness/social situations that would limit compliance with study requirements.
- 2.1.7.3 Symptomatic central nervous system metastasis.
- 2.1.7.4 Subjects unwilling to accept blood products as medically indicated
- 2.1.7.5 Pregnant women are excluded from this study because M7824 is an agent with the potential for teratogenic or abortifacient effects. Because there is an unknown but potential risk for adverse events in nursing infants secondary to treatment of the mother with M7824, breastfeeding should be discontinued if the mother is treated with these agents.
- 2.1.7.6 Patients with any active or recent history of a known or suspected autoimmune disease (with the exception of diabetes type I, vitiligo, psoriasis, or hypo- or hyperthyroid diseases not requiring immunosuppressive treatment) or recent history of a syndrome that required treatment with either systemic corticosteroids (>10 mg daily prednisone equivalent) or

immunosuppressive medications. Inhaled steroids and adrenal replacement steroid doses up to 10 mg daily prednisone equivalents are permitted in the absence of active autoimmune disease.

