### 2.2.2 Screening activities performed after a consent for screening has been signed

Screening evaluation testing/procedures are conducted under the separate screening protocol, 01-C-0129 (Eligibility Screening and Tissue Procurement for the NIH Intramural Research Program Clinical Protocols). Assessments performed at outside facilities or on another NIH protocol within the timeframes below may also be used to determine eligibility once a patient has signed the consent.

All screening tests and procedures must be performed within 21 days prior to initiation of study therapy except physical exam with skin assessment, ECOG, vital signs, blood tests and pregnancy test (repeated if >7 days):

- Complete medical history and physical examination (including height, weight, vital signs, and ECOG performance status) and skin assessment.
- Electrocardiogram (ECG)
- CT scan of chest, abdomen and pelvis with IV and PO (as indicated) contrast, or CT chest and MRI abdomen/pelvis may be performed, and [18F]-Sodium Fluoride (NaF) PET/CT bone scan (if indicated).
- Laboratory assessments: CBC with differential, acute care panel (sodium, potassium, chloride, total CO2 (Bicarbonate), creatinine, glucose, urea nitrogen), mineral panel (albumin, calcium total, magnesium total, phosphorus), hepatic panel (alkaline phosphatase, ALT/GPT, AST/GOT, total bilirubin, direct bilirubin), ionized calcium, amylase, lipase, LDH, total protein, GGT, Hepatitis B and C, PT/INR, PTT, urine analysis.
- Hepatitis B and C antibody panel
- Thyroid function tests – TSH, reflex T3 and T4
- Pre-treatment tissue biopsy and/or archival tissue availability for PD-L1 expression retrospective testing is mandatory for enrollment. PD-L1 will be performed retrospectively by EMD Serono using a test determined by EMD Serono.
- Pregnancy test for females of childbearing-potential (within 3 days prior to first dose of study drug).
- Lymphocyte Phenotyping - CD4/CD8 will be performed on known HIV-positive patients.

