## 3 STUDY IMPLEMENTATION

### 3.1 STUDY DESIGN

- This is an open label, non-randomized, single arm phase II trial of M7824 in checkpoint inhibitor naïve and refractory patients with urothelial carcinoma.
- We will plan to use a fixed dose of 1200 mg delivered IV every 2 weeks (Q2W) based on the recent NCI-led phase I dose-escalation trial of M7824 in advanced solid tumors (NCT02517398) [33]. M7824 appeared to have a manageable safety profile and early evidence of clinically efficacy. The MTD was not reached in this study at 20mg/kg and

- PD-L1 receptor occupancy and sequestration of TGF- $\beta$  isoforms 1-3 was achieved at M7284 dose levels >1mg/kg.
- A maximum of 68 evaluable subjects will be enrolled in checkpoint naïve [Cohort 1] and checkpoint inhibitor refractory [Cohort 2] patients with urothelial carcinoma of the bladder.
    - Cohort 1A: Checkpoint inhibitor naïve patients who are cisplatin-ineligible
    - Cohort 1B: Checkpoint inhibitor naïve patients who are refractory post-platinum therapy
    - Cohort 2A: Checkpoint inhibitor refractory patients with Complete Response (CR) or Partial Response (PR) as per RECIST 1.1
    - Cohort 2B: Checkpoint inhibitor refractory patients with Stable Disease (SD) or Progressive Disease (PD) as per RECIST 1.1
  - Enrollment of 2-3 patients per month is expected on this trial; thus, 2 to 3 years is anticipated as the accrual period.
  - Restaging will be performed every 2 cycles (8 weeks). Safety/tolerability analysis and secondary clinical efficacy analysis will be ongoing through cycle 4. Patients can continue study drug in all arms provided there is no confirmed evidence of progression, unacceptable toxicity or withdrawal from the study.

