## 3.3 DOSE MODIFICATIONS

### 3.3.1 M7824

M7824 is planned to be administered at 1200 mg (flat dose) every two weeks. Dosing may be delayed up to 12 weeks for toxicity or logistical reasons, including the inability of the patient to get to the clinic. Dose reductions are not allowed.

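### Read literally, Appendix A schedules no pregnancy test after Day 1 of cycle 6, although M7824 continues with no stated cycle cap

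*Combined protocol and SAP*

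**What the plan says.** Appendix A carries a row labelled "Pregnancy test 6". It is marked at screening and on Day 1 of each of cycles 1 to 6; every later cell is blank. The last treatment column, C6 D15 & Beyond, covers C6D15 and all later treatment visits together.

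The footnote to the row reads "For females of childbearing-potential (within 3 days prior to initiation of study therapy", which addresses only the time before treatment. Section 2.2.2 does the same: "Pregnancy test for females of childbearing-potential (within 3 days prior to first dose of study drug". Section 2.4 concerns whether screening tests must be repeated at baseline.

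Dosing is not limited to six cycles. Footnote 3 states that "M7824 will be delivered intravenously every 2 weeks (+/- 3 days", and the M7824 row is marked under C6 D15 & Beyond. Section 3.1 says: "Patients can continue study drug in all arms provided there is no confirmed evidence of progression, unacceptable toxicity or withdrawal from the study". Section 3.6.1 lists completion of study therapy among the reasons for removal but does not define it as a number of cycles.

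On the risk itself, exclusion criterion 2.1.7.5 says that "M7824 is an agent with the potential for teratogenic or abortifacient effects", and section 3.3.1.13 classes embryo-fetal toxicity as an important potential risk. A positive pregnancy test is a removal criterion (3.6.1), and pregnancy on study requires treatment to stop at once (8.6.1).

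**The concern.** For six cycles the protocol schedules a pregnancy test on Day 1 in addition to contraception and self-report. From cycle 7 the same drug continues at the same dose and interval, but the calendar no longer asks for the test, and no reason is given for dropping it. The calendar is the page that a site works from. A site following it literally would stop testing after C6D1, and a pregnancy arising later would meet no scheduled test.

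What is at stake is participant protection alone. The response rate, the two-stage designs, the sample size and the stopping rules do not depend on this row.

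**Working it through.** The plan states no figure to reproduce here. The check is a reading of the calendar against the other sections, followed by short arithmetic.

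**Marks in the calendar.** Splitting each row of the table into its cells gives 16 data cells per row against 15 column headings, so the alignment after C6D1 is uncertain by one cell.
- Pregnancy test: 7 marks, at screening and C1D1, C2D1, C3D1, C4D1, C5D1 and C6D1. All four cells after C6D1 are blank, so the finding does not depend on the alignment.
- M7824: marked in every cell from C1D1 through C6 D15 & Beyond, and in the cell after it.
- "History/PE incl weight and skin assessment" and laboratory assessments: both marked under C6 D15 & Beyond.
- Tumor evaluation and CT: on treatment, otherwise marked only on Day-1 visits (C3D1 and C5D1), yet both carry a footnoted mark under C6 D15 & Beyond. The calendar therefore has its own way of carrying a Day-1 item forward, and the pregnancy row does not use it.

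**Could another section supply the test?**
- Footnote 5 itemises the laboratory panel; a pregnancy test is not in it.
- Footnote 6 and sections 2.2.2 and 2.4 concern the period before or at the start of therapy.
- Section 3.3.1.13 relies on exclusion of pregnant participants and on contraception, and gives no test schedule.
- Section 8.6.1 says what to do once a pregnancy is known, not how it is found.

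No section schedules a test after C6D1.

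**When the last scheduled test falls.** Cycles last 28 days, so C6D1 = 1 + 5 × 28 = nominal study day 141.

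**Length of the stretch without a scheduled test.** Treatment duration is not given, so the number of cycles N is an assumption, shown over a range. With two doses per cycle:
- Doses from the C6D1 test to the end of treatment, counting the test-day dose = 2 × (N − 5).
- Of these, 2 belong to cycle 6, which opens with a test. Doses in cycles without a scheduled test = 2 × (N − 5) − 2 = 2 × (N − 6).

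| Cycles N | Doses from C6D1 test onward | Doses in cycles without a scheduled test |
|---|---|---|
| 6 | 2 | 0 |
| 7 | 4 | 2 |
| 13 (52 weeks) | 16 | 14 |

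These counts describe how long the schedule is silent. They do not measure the risk of a pregnancy or of fetal harm.

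**The case against.** The strongest reply is that this is a table-compression slip and that sites would not be misled. The treatment columns stand under a common heading for all 28-day cycles, the row is marked on every Day 1 shown, and the blank cell is headed by a Day-15 visit, where this row is always blank. A site could reasonably continue Day-1 testing. As an account of how the blank arose, this is probably right. It does not settle the matter, because the same column also holds C7D1 and every later Day-1 visit, and two other Day-1 rows were given a footnoted mark there. The sample schedule in section 5.2 avoids the ambiguity by heading its last on-treatment column with C6D1.

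The other reply is that little protection is lost. Contraception is required throughout treatment and for at least 65 days afterwards in women; a woman who suspects pregnancy must tell her physician at once (2.1.1.11); examination and laboratory visits continue; the team discusses each patient weekly during active treatment (7.4.1); and nothing in 3.6.1 limits removal to a positive result from a scheduled test. All of this stands and keeps the point small. None of it is a scheduled test.

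A reader might infer that the sponsor decided to stop testing after cycle 6, or that women are left unprotected from then on. The documents support neither reading: they give no rationale for stopping, and the other safeguards continue.

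**Conclusion.** The gap holds as a matter of text: no pregnancy test is scheduled after C6D1, nominal day 141, while M7824 may continue with no stated cycle cap. It is a minor point of participant safety that is worth correcting because the correction is cheap.

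Three limits apply. That the blank is an oversight is an inference, which the documents neither confirm nor exclude. The absence of a cap rests on section 3.1 and on completion of therapy being undefined in 3.6.1; the & Beyond heading confirms that treatment past cycle 6 is foreseen. The number of women of childbearing potential is not given; that it will be small is an expectation, not a documented figure.

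The test schedule within cycles 1 to 6 is not in question.

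**What to change.** Make two edits in Appendix A. Put a footnoted mark in the pregnancy-test row under C6 D15 & Beyond. Amend footnote 6 so that, for females of childbearing potential, it keeps the existing 3-day window before the start of therapy and then adds: on Day 1 of every cycle while M7824 is given. Both edits are needed, because a mark pointing to the present footnote would refer to a rule that covers only the time before treatment.

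The cost is one extra pregnancy test per woman of childbearing potential per cycle after cycle 6, that is N − 6 tests: none at 6 cycles, 1 at 7 and 7 at 13. Each falls at a visit where laboratory samples are already drawn. No Day-15 test is added, and contraception and the removal rules stay as they are.

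The edit does not add a test at the end of treatment, so the doses of the last cycle would still have no later test. The sponsor could settle that separately in the same footnote.
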